12.2.3. Audit/Inspections

Authorized representatives of Sebela, a regulatory authority, or an Independent Ethics Committee (IEC) may visit the site to perform audits or inspections, including source data verification. The purpose of a Sebela audit or inspection is to systematically and independently examine all study-related activities and documents to determine whether these activities were conducted, and data were recorded, analyzed, and accurately reported according to the study protocol, GCP guidelines of the International Conference on Harmonization (ICH), and any applicable regulatory requirements. The Investigator should contact Sebela immediately if contacted by a regulatory agency about an inspection.

12.3. Pharmacokinetic Sample Handling & Shipping

The procedure for pharmacokinetic sample collection, storage and shipping and the required supplies are provided in the study's Sample Collection Manual. Serum samples collected in the study will be shipped to the analytical lab for analysis per the procedures outlined in the Sample Collection Manual.

13. ETHICAL AND LEGAL CONSIDERATIONS

Study information from this protocol will be posted according to regulatory guidelines before enrollment of subjects begins.

The final study protocol, including the final version of the ICF, must be approved in writing by an IEC. The Investigator must submit written approval to Sebela before he or she can enroll any patient/subject into the study.

The Principal Investigator is responsible for informing the IEC of any amendment(s) to the protocol in accordance with local requirements. In addition, the IEC must approve all advertising used to recruit patients for the study. The protocol must be re-approved by the IEC upon receipt of any amendments and annually, according to local regulations.

The Principal Investigator is also responsible for providing the IEC with reports of any reportable SAEs from any other study conducted with the investigational product. Sebela will provide this information to the Principal Investigator.

Progress reports and notifications of SAEs will be provided to the IEC according to local regulations and guidelines.

The Principal Investigator(s) at each center will ensure that the patient is given full and adequate oral and written information about the nature, purpose, possible risk and benefit of the study. Patients must also be notified that they are free to discontinue from the study at any time. The patient should be given the opportunity to ask questions and allowed time to consider the information provided.

The patient's signed and dated ICF must be obtained before conducting any study procedures.

The Principal Investigator(s) must maintain the original, signed ICF. A copy of the signed ICF must be given to the patient.

Appendix 1. Time and Events Schedule

Visit	Screening	Enrollment/IUD Placement	Clinic PK Visits		Clinic PK Visits (VeraCept Subjects ONLY)	Month 60 OR Exit Visit
Day	Day -28 to 1	Day 1	Day 3 (±24 hrs)	Days 8, 15, 22, 29 (±1 day) Day 57⁶ (±3 days)	Months 6, 12, 18, 24, 30, 36 and 48 (±30 days)	Month 60 (±30 days) OR Exit Visit
Assessment of Eligibility	X	X				
Distribution of subject materials (if applicable)	X					
Informed Consent/Accent/PHI and Bill of Rights	X					
Demographics and baseline characteristics	X					
Medical/surgical, gynecologic and menstrual history	X					
Vital signs and weight	X	X	X	X	X	X
Height	X					
General physical exam	X					
Pelvic exam (string check if post IUD insertion)	X	X ¹		X	X	X
Cervical cytology	X					
Cervical infection tests	X ^{2,3}					
Transvaginal ultrasound, only if clinically indicated		X		X	X	X
Pregnancy test – urine	X	X				X
Prior and concurrent medication	X	X	X	X	X	X
Adverse events	X	X	X	X	X	X
IUD placement		X				
IUD removal						X ⁷
Concomitant contraception		X				X
Subject education – need for contraception	X	X	X	X	X	X
Blood draw for PK analysis (serum copper sample)	X ⁴	X ⁵	X ⁵	X ⁵	X ⁵	X ⁵

1. Pelvic exam for IUD string check by palpation or visualization.
2. Screening for cervical infection tests are to be done at screening unless these tests have been previously completed within 3 months of the screening visit and were negative. If a subject tests positive prior to IUD insertion, the subject should be treated prior to IUD placement. The subject may be inserted 7 days post-treatment. A cervical infection retest should be done 3-months post-IUD insertion to assure there is not a case of re-infection.
3. Insertion can occur without receipt of test results if there is no clinical evidence of infection. If, after IUD insertion, the screening cervical infection test results are positive, the subject should be treated. A cervical infection retest should be done 3 months post-treatment.
4. Subjects will be screened within 60 days prior to the first insertion of study drug, , and two blood samples will be collected within 28 days from Day 1, and at least 24 hours apart within this screening period (can be performed on Screening and Day 1 visit prior to IUD insertion). to establish baseline copper concentrations.
5. On Day 1, collect blood samples for pharmacokinetic analysis prior to intrauterine insertion. On Day 3, collect samples 48 hours ±24 hours after IUD insertion. PK samples on Day 8, 15, 22, and 29 should be collected within 1 day of the planned collection day while Day 57 should be collected within 3 days of planned collection day, at

approximately the same time as the Day 3, 48-hr \pm 1 day PK sample collection. Following the PK collections on Day 57, the PK samples should be collected within 30 days of the planned collection day

6. Paragard subjects will have Exit Visit procedures completed on Day 57
7. ParaGard subjects may continue ParaGard use per standard clinical care or have the device removed.

1. INTRODUCTION

This pharmacokinetic analysis plan describes the analysis and reporting of the pharmacokinetic (PK) results for study CMDOC-0045, in which the bioavailability of systemic copper exposure after insertion of Sebela's investigational VeraCept intrauterine contraceptive device (IUD) is compared to the marketed ParaGard IUD in healthy, post-menarcheal women.

Sebela has developed VeraCept to provide a long-acting, reversible method of contraception for non-pregnant, parous, and nulliparous women of child-bearing age. VeraCept's design utilizes a shape memory nitinol spring frame with the same active chemical entity as the marketed reference product, ParaGard (99.99% pure copper), yet containing less than half of the exposed copper surface area (175 mm²). VeraCept is delivered preloaded in an introducer, which is narrower than the ParaGard inserter, to simplify clinician insertions and facilitate correct, easy placement in the uterus. Correct placement and a shape memory frame optimize VeraCept's long-term efficacy by decreasing expulsions and increasing its tolerability, thereby improving end-user continuation rates. In contrast to the passive plastic "T" utilized in ParaGard, VeraCept has been designed to mitigate the side effects associated with ParaGard without compromising contraceptive effectiveness.

The current study will assess systemic copper exposure after insertion of VeraCept as compared to ParaGard in enrolled subjects. The study will characterize the PK and comparative bioavailability of observed and baseline-corrected total serum copper exposure in patients after receiving either VeraCept or ParaGard.

This is a 3-part analysis plan with Part A addressing the planned interim PK analysis, Part B addressing the noncompartmental analysis (NCA) and statistical analysis of the PK data for the Treatment Comparison Phase and resulting final PK report, and Part C addressing the analyses on PK data collected during the Extension Phase.

In addition to PK analysis and reporting, the study will also monitor the safety of VeraCept and ParaGard in enrolled subjects. The safety sections of this PK analysis plan address the planned summary and reporting of the safety data for this study but detailed information, including the list of planned safety data summary tables and listings, can be found in the safety analysis plan authored by Synteract. The safety data summary tables and listings and the resulting safety conclusions will be generated by Synteract and will be included in the final PK report.

2. PHARMACOKINETIC OBJECTIVES

This analysis plan is based on the information provided in Protocol Version 2.0 (03 Jul 2019).

2.1 Primary Objective

The primary objective of the study related to the PK analysis is:

- To assess the relative bioavailability of observed systemic copper from VeraCept versus ParaGard based on Cmax, Cmean, and AUC0-56 days.

2.2 Secondary Objectives

The secondary objectives of the study related to the PK analysis are:

- To assess the relative bioavailability of baseline-corrected total serum copper from VeraCept versus ParaGard based on Cmax, Cmean, and AUC0-56 days.
- To assess the total serum copper levels within each treatment relative to the normal range (49 to 184 $\mu\text{g}/\text{dL}$).
- To assess the long-term stability of copper levels following insertion of VeraCept.

3. STUDY ENDPOINTS

3.1 Primary Endpoint

The primary endpoint related to the PK analysis is:

- Mean total serum copper concentration (Cmean), Cmax, and AUC0-56 days for observed copper for each treatment.

3.2 Secondary Endpoints

The secondary endpoints related to the PK analysis are:

- Mean total serum copper concentration (Cmean), Cmax, and AUC0-56 days for baseline-corrected copper for each treatment.
- Total serum copper concentrations within each treatment for each assessment day for 56 days.
- Mean total serum copper concentration for observed and baseline-adjusted copper for each treatment over 5 years (Treatment A, VeraCept IUD only).

[figure not shown]
4. INVESTIGATIONAL PLAN

4.1 Overall Study Design

[figure not shown]
This parallel, open-label study is designed to evaluate the comparative bioavailability of systemic copper exposure after insertion of VeraCept versus ParaGard in post-menarcheal women. Up to 40 subjects will receive one of two treatments (A or B) as described below:

- Treatment A (N=20): VeraCept[®] IUD, test (referred to as VeraCept)
- Treatment B (N=20): ParaGard[®] IUD, reference (referred to as ParaGard)

[Figure 1](#) and [Figure 2](#) display the study design schematic for the Treatment Comparison Phase and Extension Phase, respectively.

Figure 1 Study Design Schemata — Treatment Comparison Phase

Subjects will be screened within 60 days prior to the first insertion of study drug, and blood samples will be collected within 28 days from first insertion of study drug at two visits within this screening period to establish baseline copper concentrations. At least 24 hours should separate each baseline sample. On Day 1 of each treatment period, PK, safety, and baseline assessments will be collected prior to IUD insertion. Subjects will return to the clinic at 48 hours post-IUD insertion (Day 3(± 24 hours)), and on Days 8 (± 1 day), 15 (± 1 day), 22 (± 1 day), 29 (± 1 day), and 57 (± 3 days) for blood collection for measurement of total serum copper concentrations.

Figure 2 Study Design Schemata — Extension Phase

On Day 57, ParaGard subjects will exit the study and may continue ParaGard use per standard of clinical care. VeraCept subjects will continue in the extension phase of the study, intended to assess long-term stability of serum copper concentrations up to 5 years and monitor safety. During the first 3 years, subjects will return to the clinic every 6 months (± 30 days) for clinical assessments and blood collection for measurement of total serum concentrations. Following Year 3, subjects will return annually, up to Year 5. During the extension phase, PK collections may occur anytime within 30 days of the planned collection time. Subjects prematurely discontinuing the study should follow the Early Discontinuation procedures specified in the protocol. Additional follow-up visits may be scheduled, as needed, if a subject has an ongoing significant adverse event (AE) and/or a clinically significant laboratory abnormality. A schedule of the study procedures and assessments to be conducted for each subject is provided in the Time and Events Table in the protocol.

Subjects will be randomized to a treatment group (VeraCept or ParaGard). The study will be conducted at one or more study sites. Participants will be randomly allocated in a 1:1 ratio, either to VeraCept or ParaGard. The randomization will be stratified by site, if needed, but centrally managed until 40 subjects have been randomized.

5. PHARMACOKINETIC SAMPLE COLLECTION

5.1 Blood Collection and Sample Processing

Two blood samples for PK analysis will be collected within 28 days from Day 1, and at least 24 hours apart within this screening period (can be performed on Screening and Day 1 visits prior to IUD insertion) to establish baseline copper concentrations, on Day 1 prior to IUD insertion, on Day 3, approximately 48 hours after insertion, and on Days 8, 15, 22, 29, and 57 at approximately the same time of day as the prior PK collections. Following the PK collections on Day 57, the PK samples for Months 6, 12, 18, 24, 30, 36, and 48 will be collected within 30 days of the planned collection day. Approximately 3-5 mL of whole blood will be collected for each blood draw. The total volume collected from each subject for all PK samples will be approximately 20 mL.

Blood samples will be collected in containers appropriate for serum collection, such as a “red topped” tube, which does not contain an anticoagulant.

5.2 Bioanalytical Methods for Pharmacokinetic Samples

Blood samples will be processed for serum as described in the PK laboratory manual. The yield of serum will be subdivided into 2 samples (~1 mL each). One of these samples will be shipped as soon as possible to the analytical lab for analysis of total serum copper, and the other will be stored at -20°C at the site until completion of the study (or until directed by Sebela or designee), and then sent to the analytical lab in one group.

6. PHARMACOKINETIC POPULATION

6.1 Pharmacokinetic Population

The PK study population is defined as all randomized subjects for which all pre-insertion total serum copper concentrations were within the normal range (49 to 184 µg/dL), had an IUD placed successfully, and completed all scheduled PK sample collections without a protocol deviation or AEs that significantly impact the planned PK analyses.

6.2 Changes to Protocol-Specified Population

The protocol defines the overall PK study population but not the PK concentration and PK parameter populations.

The PK concentration population is defined as all randomized subjects that have an IUD placed successfully and have at least one quantifiable total serum copper concentration post-insertion. Concentration data from this population will be presented in the tables and used in the calculation of summary statistics for plotting purposes.

The PK parameter population is defined as subjects in the PK concentration population with sufficient data to calculate PK parameters (at least 4 quantifiable total serum copper concentrations and no protocol deviations that have a material impact on the PK). This population will be included in the NCA and individual copper concentration versus time figures.

Any other changes to protocol-specified population due to protocol deviations or other factors that may impact PK will be detailed in the final PK report.

7. PART A – INTERIM PHARMACOKINETIC AND STATISTICAL ANALYSES DURING TREATMENT COMPARISON PHASE

7.1 Noncompartmental Pharmacokinetic Analysis and Descriptive Statistics

An interim analysis for the Treatment Comparison Phase will be performed once approximately 20 subjects have completed the visit on Day 57. All interim PK analysis and reporting will be performed according to applicable Nuventra standard operating procedures and protocol specifications. PK parameters will be calculated by Nuventra using Phoenix® WinNonlin® 8.1 or later (Certara, Princeton, NJ, USA) using nominal doses and sampling times.

For these analyses, all relevant PK parameters from Section 8.1 and Tables, Listings, and Figures from Section 11 will be generated using Phoenix® WinNonlin®.

The mean of the two screening baseline values and the Day 1 pre-dose concentration will be used for baseline correction. Descriptive statistics (number of subjects [N], mean, standard deviation [SD], percent coefficient of variation [CV%], median, minimum, and maximum) will be used to summarize observed and baseline-corrected serum concentrations. All relevant parameters will be summarized using descriptive statistics (N, mean, SD, CV%, median, minimum, maximum, geometric mean, and geometric CV%). Parameters that are equal to zero will be reported as “missing”.

No statistical analyses are planned for interim analyses.

8. PART B – FINAL PHARMACOKINETIC AND STATISTICAL ANALYSES DURING TREATMENT COMPARISON PHASE

8.1 Noncompartmental Pharmacokinetic Analysis and Descriptive Statistics

All final PK analysis and reporting for the Treatment Comparison and Extension Phases will be performed according to applicable Nuventra standard operating procedures and protocol specifications. PK parameters will be calculated using NCA implemented within a validated installation of Phoenix® WinNonlin® using actual dosing and sampling times. Programming of tables, figures, and listings will be performed using verified templated R code run in validated R Software and RStudio environments. Additional information on the software to be utilized in this study can be found in [Table 8-1](#). The actual version of the software will be included in the final PK report. Additional software may be used, if necessary. All software used will be documented in the final PK report.

Table 8-1. Software List

Software	Use	Version	Company
Phoenix WinNonlin	NCA	V 8.1 or later (Validated as per VAL.001.04)	Certara (Princeton, NJ)
R Software	Input file generation	V 3.4.0 or later (custom code)	R Foundation for Statistical Computing (Vienna, Austria)
	TLFs	V 3.4.0 or later (Validated as per VAL.002.07)	
RStudio	TLFs	V 1.0.143 or later (Validated as per VAL.002.07)	RStudio (Boston, MA)
SAS	Biostatistics	SAS 9.4 or later	SAS Institute, Inc. (Cary, NC)

PK blood samples will be analyzed for total serum copper concentrations using validated bioanalytical methods. The mean of the two screening baseline values and the Day 1 pre-dose concentration will be used for baseline correction.

Descriptive statistics to summarize observed and baseline-corrected serum concentrations include: N (number of non-missing data), Mean (arithmetic mean), standard deviation (SD), arithmetic percent coefficient of variation (CV%), minimum, median, and maximum.

Summaries of plasma concentration data will include data for all subjects in the PK concentration population (see Section 6.2).

PK parameters for uncorrected and baseline-corrected serum copper will be calculated as described in [Table 8-2](#).

Table 8-2. Pharmacokinetic Parameters

Parameter	Description
Data from Treatment Comparison Phase	
Cmax	Maximum observed concentration, observed by inspection of individual study participant serum concentration-time plots
Tmax	Time of maximum observed concentration, obtained directly from the observed concentration-time data
Cmean	Mean total serum copper concentration of samples collected after Day 1 (Days 3-57)
AUC0-56 days	Area under the concentration time curve, from time 0 (study Day 1) to the last measurable non-zero concentration up to 56 days (study Day 57), calculated by the linear trapezoidal method

Note that the abbreviations and definitions listed above may differ slightly from the protocol in the phrasing; however, the equations and methods used to generate these parameters do not differ from the protocol.

Additional PK parameters may be calculated, as necessary, to fully characterize the PK profiles of uncorrected and baseline-corrected serum copper and will be defined in the final PK report.

No PK parameters will be calculated for subjects with fewer than 4 quantifiable total serum copper (uncorrected) concentrations following imputation of concentrations below the limit of quantification (BLQ) (see Section 8.4). Baseline-corrected copper PK parameters will be calculated for all subjects regardless of the number of non-zero concentrations.

All subjects in the PK parameter population (see Section 6.2) will be included in the descriptive statistics for the PK parameters. PK parameters will be listed for each subject by treatment, and the following descriptive statistics will be provided: N (number of subjects with non-missing data), arithmetic mean, SD, CV%, median, minimum, and maximum. Geometric mean and geometric CV% will be calculated for continuous PK parameters. Tmax will be presented as N, median, minimum, and maximum. Parameters that are equal to zero will be reported as “missing”.

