11.1. Determination of Sample Size

The assumption is that there is no additional systemic exposure of copper when using the IUD. The primary analysis will use uncorrected total serum copper parameters (Cmax, Cmean, AUC0-56 days). A secondary analysis will be conducted using baseline-corrected total serum copper parameters (Cmax, Cmean, AUC0-56 days).

For the analysis using Cmax and Cmean, no formal hypothesis testing is being done. As such, a precision approach will be taken with boundaries chosen to reflect typical BE boundaries in the ln scale (plus or minus 22%). Assuming a normal range of 49 to 184 $\mu\text{g/dL}$, an estimate of the normal (mean) value could be close to 110-120 $\mu\text{g/dL}$. A comparable boundary would be plus or minus 22. This estimated mean with the added half-width still falls well within the normal range.

For the analysis using AUC0-56 days, no formal hypothesis testing is being done. As such, a precision approach will be taken with boundaries chosen to reflect typical BE boundaries in the ln scale (plus or minus 22%). AUC values will be ln transformed.

For a two-sided 90% confidence interval for a two-sample normal mean difference, assuming a common standard deviation of 25, a sample size of 12 per group is required to obtain a half-width of at most 22 $\mu\text{g/dL}$ with a conditional probability of at least 0.90 given that the interval contains the true mean difference. The actual probability is 0.95.

Assuming a maximum unevaluable rate of 40%, up to 20 subjects will be enrolled in each group. Replacement subjects may be enrolled, as needed, to ensure that at least 24 evaluable subjects complete the study

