11.4. Pharmacokinetic Analyses

11.4.1. Pharmacokinetic Methods

Pharmacokinetic blood samples will be analyzed for total serum copper concentrations using validated bioanalytical methods. The mean of the 2 screening baseline values and the Day 1 pre-dose concentration will be used for baseline-correction.

Baseline-corrected serum concentrations that are less than zero will be treated as zero in the computation of mean baseline-corrected serum concentration values and derivation of individual subject computed parameters. Descriptive statistics (number of subjects, mean, standard deviation [SD], CV%, median, minimum, and maximum) will be used to summarize observed and baseline-corrected serum concentrations.

Both baseline corrected and observed post-dose copper concentrations will be used for calculation of relevant serum PK parameters (e.g., Cmax, Cmean, AUC0-56 days) using standard non-compartmental methods and actual sampling times utilizing a PK data analysis program (e.g., Phoenix WinNonlin® or equivalent). A linear trapezoidal method will be used to estimate the area under the curve. All relevant parameters will be summarized using descriptive statistics (number of subjects, mean, standard deviation [SD], CV%, median,

minimum, maximum, geometric mean, geometric CV%). Parameters that are less than or equal to zero will be treated as “missing”.

PK Parameters to be calculated will include:

Cmax	Maximum observed concentration
Tmax	Time of maximum observed concentration
Cmean	Mean total serum copper concentration of samples collected after Day 1 (Days 3-57)
AUC0-56 days	The area under the concentration time curve, from time 0 (study Day 1) to the last measurable non-zero concentration up to 56 days (study Day 57), calculated by the linear trapezoidal method.

Total serum copper concentration and pharmacokinetic data will be listed and presented in graphical form and will be summarized descriptively by treatment group.

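### The documents disagree on whether the Day 1 pre-insertion copper value can count as a woman's Cmax or Tmax; the SAP rows should limit both to post-insertion samples

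*SAP*

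**What the plan says.** PK SAP 8.1, Table 8-2, defines four parameters.

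- The Cmax row reads "Maximum observed concentration, observed by inspection of individual study participant serum concentration-time plots" and does not say which samples are eligible.
- The row for Tmax is equally silent: it takes the time of that maximum straight from the profile.
- By contrast, the row for Cmean sets a limit: "Mean total serum copper concentration of samples collected after Day 1 (Days 3-57").
- The row for AUC reaches back to the pre-insertion point: "Area under the concentration time curve, from time 0 (study Day 1) to the last measurable non-zero concentration up to 56 days".

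Only the Cmean row excludes the pre-insertion sample. The Cmax and Tmax wording is repeated for the combined phases in PK SAP 9.1 (captioned Table 9-1, called Table 9-2 in the text).

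Protocol 11.4.1 states: "Both baseline corrected and observed post-dose copper concentrations will be used for calculation of relevant serum PK parameters", and names Cmax, Cmean and AUC as examples. The matching sentence in the protocol synopsis (Criteria for Evaluation) drops the word *post-dose*. The protocol's own Cmax row in 11.4.1 has no sampling limit either.

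The PK SAP says in 8.1 that its analysis follows the protocol and that its methods do not differ from it, and in 8.3 that no change to the protocol-defined analysis is planned. The primary model (PK SAP 8.2) is an ANCOVA of uncorrected Cmax, Cmean and AUC on treatment and the Day 1 pre-insertion concentration.

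**The concern.** For most drugs the pre-dose concentration is near zero and cannot be the maximum, so an unlimited Cmax definition does no harm. Copper is endogenous. Protocol 11.1 expects a normal mean near 110 to 120 µg/dL and adds: "The assumption is that there is no additional systemic exposure of copper when using the IUD". On that assumption the pre-insertion value competes on equal terms with each later value.

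Where it wins, the Cmax outcome is the same number as the ANCOVA covariate and says nothing about the device. Her Tmax falls at time 0, and because PK SAP 8.1 reports parameters equal to zero as missing, the Tmax summary could hide these cases. The same applies to baseline-corrected Cmax: baseline is the mean of three pre-insertion values, so a Day 1 value above that mean stays positive after correction and can be the maximum.

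Two programmers could follow these documents faithfully and obtain different values of a primary parameter.

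**Working it through.** **1. The plan's own figure.** Protocol 11.1 gives 12 per group for a 90% confidence interval half-width of at most 22 µg/dL at SD 25, with probability 0.95 conditional on the interval containing the true difference. Integrating over the distribution of the pooled SD (22 degrees of freedom) gives 0.954 at n = 12 and 0.897 at n = 11. Inflation gives 12 / (1 − 0.40) = 20 per group. Both figures reproduce, and neither depends on this point.

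**2. How often the pre-insertion value would be Cmax.** The comparison phase has one Day 1 pre-insertion sample and six later ones (Days 3, 8, 15, 22, 29, 57). If neither device changes copper and the seven values are exchangeable:

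- P(Day 1 is the largest) = 1/7 = 14.3%, or 12/7 ≈ 1.7 of 12 women per arm.
- P(at least one among 24 evaluable women) = 1 − (6/7)^24 = 97.5%.
- With serially correlated values (exponential decay, 2 to 28 days) the chance is 12.6 to 13.6%.
- With a post-insertion rise of 0.5 or 1 within-woman SD it falls to 6.8% or 2.6%.
- For the combined-phase Cmax there are 6 + 8 = 14 later samples, so it is 1/15 = 6.7%. That Cmax is for VeraCept only, and no treatment comparison is planned for it.

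**3. Effect on the level of Cmax.** The expected maximum of seven standard normal values is 1.352, and of six 1.267. The difference, 0.085 within-woman SDs, is 0.5, 0.8 and 1.3 µg/dL at within-woman SD 6, 10 and 15. It applies to any arm in which copper does not change.

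**4. Effect on the treatment comparison.** The planned ANCOVA was simulated with 12 per arm, total SD 25 (protocol 11.1), independent within-woman values, and a post-insertion rise in one arm only (40,000 trials per setting). The within-woman SD is an assumption, shown as a range. Each cell gives the result with Day 1 eligible for Cmax, then with Day 1 excluded.

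| Within-woman SD (µg/dL) | Estimate, true rise 5 | Dilution | Estimate, true rise 10 | Dilution | 90% half-width, no rise |
|---|---|---|---|---|---|
| 6 | 4.59 vs 5.00 | 8% | 9.49 vs 9.99 | 5% | 4.41 vs 4.97 |
| 10 | 4.45 vs 4.96 | 10% | 9.27 vs 9.99 | 7% | 7.08 vs 7.97 |
| 15 | 4.46 vs 5.02 | 11% | 9.15 vs 10.04 | 9% | 9.80 vs 10.97 |

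Dilution is one minus the ratio of the two estimates. It arises because the pre-insertion value still wins in about 1 in 7 women in the unchanged arm but seldom in the arm that rises. With no rise, the mean estimated difference is about zero under both definitions, and the half-width ratio is 7.08/7.97 = 0.89 at SD 10 (0.89 at the other two SDs as well), so about 11% narrower. Across the nine settings, coverage of the true post-insertion difference is 89.4 to 90.3% with Day 1 eligible and 89.7 to 90.2% with it excluded.

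**The case against.** The strongest reply is that the rule already exists. Protocol 11.4.1 says post-dose concentrations are used and names Cmax, and the PK SAP says that it follows the protocol. AUC, with its explicit time-0 start, can be read as the one stated exception. This stands in part: it would be wrong to say flatly that the plan leaves Cmax unrestricted. It does not settle the matter. The protocol sentence also covers AUC and so cannot be applied literally to every parameter it names, the synopsis omits the word, and the SAP rows that will be programmed omit it while their neighbour states a limit.

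The second reply is that the effect is small, and that the 1 in 7 and the dilution belong to different situations. This stands. The full 1 in 7 applies in both arms only when neither device changes copper, and then there is no difference to bias. It rests on the wording in protocol 11.1; the synopsis assumes only no additional exposure with VeraCept compared with ParaGard, which is not enough. When one device does raise copper, the frequency drops in that arm and the loss is a fraction of a µg/dL in the settings above, against a planned half-width of 22 µg/dL and no formal hypothesis test.

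A reader might infer that 1 in 7 women will be misclassified and that the comparison or its interval is invalid. The documents do not support that, because the post-dose sentence may be applied as intended, and coverage is kept even if it is not. A reader might also picture copper falling after insertion, which would make pre-insertion maxima more frequent. Nothing in the documents predicts a fall, and protocol 1.1 says that release causes no significant change in serum copper, so no figure is given for it.

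**Conclusion.** The point holds as an inconsistency in the definition of a primary parameter. The protocol synopsis, protocol 11.4.1 and PK SAP Tables 8-2 and 9-1 do not together say whether the Day 1 pre-insertion value may be Cmax.

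If the SAP rows are applied as written, there is no bias and no loss of coverage when neither device changes copper, but the interval is about 11% narrower. That gain comes from sharing a value with the covariate, not from more information on exposure. A true one-arm rise of 5 to 10 µg/dL is diluted by about 5 to 11%. Both effects lean towards showing similarity in a study meant to maximise the ability to detect a difference (protocol 1.2). The 1 in 7 needs exchangeable samples and no change in copper; the dilution and interval figures also need the assumed within-woman SD of 6 to 15 µg/dL. The effect is modest, but the ambiguity is worth removing because the remedy costs so little.

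**What to change.** In PK SAP Tables 8-2 and 9-1 and in protocol 11.4.1, define Cmax and Tmax, for observed and baseline-corrected copper, as the largest concentration, and its time, among samples collected after IUD insertion: Days 3 to 57 for the treatment comparison, and Day 3 to Month 60 for the combined phases. Align the synopsis sentence. State that the Day 1 pre-insertion value is kept as the time-0 point of AUC, the ANCOVA covariate and one of the three baseline values.

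The cost is a sentence in each place and one filter in the analysis dataset, with no new data. Cmax will be slightly lower in some women, and the Cmax interval slightly wider.
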